Screening process will take place at Visit 1, up to 14 days prior to placebo run in treatment.

Visit 1 (up to week -4)

- Medical history
- Medication history
- Complete Physical examination (PE)
- ECG
- Vital signs (blood pressure, heart rate). Vital signs will be measured in the sitting position after at least 5 minutes of rest.
- Clinical laboratory evaluations
 - Chemistry: Electrolytes, BUN, creatinine, glucose level, liver function tests (LFT) including transaminases (ALT, AST), albumin, and alkaline phosphatases, creatine phosphokinase (CPK)
 - Hematology: Complete blood count (CBC)

Run-in Phase (to week -2)

The run-in phase will consist of 2 weeks period starting at visit (Visit 2) week -2

Visit 2

- Informed consent
- Medication history
- Brief physical examination
- Treatment (run in placebo)
- Vital Signs
- Self-monitored fasting morning blood glucose (finger-stick) of fasting blood glucose will be recorded in the patient diaries 3 days weekly in the morning.

Treatment Phase (week 0)

The Treatment Phase will consist of a treatment period of 12 weeks that will start at visit 3 (week 0) and outpatient visits at week 1, 2, 4, 8, and 12 (final visit).

At each visit patients will have

- Medication history
- Brief Physical examination (PE)- at Visits 4,5, 6, and 7
- Treatment
- Medication Compliance
- Vital signs (blood pressure, heart rate). Vital signs will be measured in the sitting position after at least 5 minutes of rest.

At Visits 3 (baseline), 6, 7, and 8, patients will have

- Clinical laboratory evaluations (chemistry, hematology)
- Fasting blood glucose and insulin (also used for HOMA estimates)²
- Self-monitored fasting morning blood glucose (finger-stick) of fasting blood glucose will be recorded in the patient diaries 3 days weekly in the morning.
- Adiponectin

At Visits 3 and 8 Patients will have

- Complete PE
- FibroMax Test
- Fibroscan
- MRI PDFF

End-of-Study (EOS) (week 16) /Early Discontinuations

The EOS visit (Visit 9) will be conducted 4 weeks following the last scheduled treatment visit. Patients will complete the following EOS evaluations:

- Medication history
- Complete PE, only if the investigator deems it necessary.
- EOS ECG, only if the investigator deems it necessary.
- Vital signs (blood pressure, heart rate) will be measured in the sitting position after at least 5 minutes of rest, only if the investigator deems it necessary.
- Clinical laboratory evaluations (chemistry, hematology)
- Fasting blood glucose

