- Fasting blood Insulin
- Adiponectin

Patients who are discontinued early from the study will complete the EOS evaluations at the time of early discontinuation.

Unscheduled visit

The patient may be required to return for an unscheduled visit for a repeat measurement of fasting blood glucose, if the investigator deems it necessary.

² HOMA = The Homeostasis Model Assessment

Self-Monitoring Fasting Blood Glucose and Patient Diaries

All patients will self-monitor fasting morning blood glucose levels three (3) times weekly during the run-in and treatment period. Monitoring must be performed at the same time each designated day (\pm 10 minutes) prior any caloric intake. Patients will be required to record the values in a patient diary and bring the diary to each clinic visit; Information recorded for the fasting blood glucose will be reviewed by the clinical research coordinator for completeness and transcribed onto CRF's. During the study, both fasting finger stick glucose and laboratory fasting plasma glucose will be obtained.

If a fasting blood glucose measures greater than or equal to 270 mg/dL (15 mmol/L) during daily self-monitoring or during any in-clinic visit, the patient will be required to contact the clinic to report the value. Blood will be drawn and sent to lab for plasma glucose determination. The patient may be required to return for an unscheduled visit to the clinic for a repeat measurement of fasting blood glucose within one week after the original measurement. If the repeat measurement is also greater than or equal to 270 mg/dL, the patient will be discontinued from treatment with study drug and offered rescue medication. The patient will continue to be seen for all remaining study visits, if possible.

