Fingerstick glucose values of <50 mg/dL (2.78 mmol/L) should be confirmed by laboratory plasma glucose measurements and if three or more are observed within 12 hours subsequent to administration of study drug without a reasonable explanation (such as increased physical activity and/or skipped meal), the patient will be discontinued from treatment with study drug and rescued with glucose administration (20g of glucose tablets) which will be available at all times at the study site. This information will be recorded in the patient's diary and the patient will be instructed to contact the study site if this occurs. The patient will continue to be seen for all remaining study visits. Sites will instruct patients to immediately perform a finger stick glucose measurement if any symptoms occur that may be related to hypoglycemia (e.g., weakness, dizziness, shakiness, increased sweating, palpitations, or confusion), and to avoid delay in treating these symptoms. The measurements will be recorded in the patient diary. Patients will always carry glucose tablets with them and ingest 3-4 tablets if hypoglycemia occurs.

Hypoglycemia and associated symptoms (e.g., weakness, dizziness, shakiness, increased sweating, palpitations, or confusion), have been associated with insulin administration, including ORMD-0801.

Table 1: Schedule of Assessments

Assessments	Screening	Placebo	Treatment						Un Scheduled Visit	End-of-Study / Early Termination
			0	1	2	4	8	12		
Week	up to -4	-2	0	1	2	4	8	12	Not Defined	16
Days	Up to -28	-14	7± 2	7± 2	14± 2	28± 2	56± 2	84± 2		112±2
Visit	1	2	3	4	5	6	7	8	Un Scheduled	9
Written informed consent	X									
Medical history	X									
Medication history	X	X	X	X	X	X	X	X		X
Complete physical examination	X		X					X		(X ¹)
Brief physical examination		X	X	X	X	X	X	X		
Treatment		X	X	X	X	X	X			
Medication compliance check			X	X	X	X	X	X		
ECG	X									(X ¹)
Vital signs	X	X	X	X	X	X	X	X		(X ¹)
Clinical laboratory evaluations ²	X		X			X	X	X	(X ¹)	X
Fasting blood glucose ³		X	X			X	X	X	(X ¹)	X
Fasting Insulin ³		X	X			X	X	X		X
Self-monitored fasting morning blood glucose ⁴		X	X	X	X	X	X	X		
Adiponectin			X			X	X	X		X
FibroMax Test			X					X		
Fibroscan Test			X					X		
MRI PDFF			X					X		

¹Only if investigator deems necessary

²Chemistry (electrolytes, BUN, creatinine, glucose, LFTs) and CBC

³Fasting blood glucose and insulin will be used to determine HOMA estimates.

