⁴Self-monitoring (finger-stick) of fasting blood glucose will required 3 days weekly in the morning and recorded in patient diaries.

TREATMENT REGIMEN

The treatment regimen will consist of a soft gelatin capsule containing 8 mg insulin, and 75 mg SBTI. Patients will take 2 capsules daily in the morning with or without food.

SAFETY EVALUATIONS

See complete instructions about Safety and Adverse Events evaluation and reporting in **Appendix B**.

- Adverse events will be collected throughout the study beginning from the time the patient signs the consent form until the EOS evaluations
- Concomitant medications/therapies will be recorded throughout the duration of study, beginning from the time the patient signs the informed consent.
- Vital signs (blood pressure, heart rate) will be measured in the sitting position after at least 5 minutes of rest at all visits
- Clinical laboratory evaluations (chemistry, hematology) will be performed at screening and at weeks 0, 4, 8, 12, and 16.
- Treatment of significant hyperglycemia, will be tailored to the medical history and needs of the patient, as per recommended treatment guidelines.
- Symptomatic hypoglycemia - Hypoglycemia as noted by a feeling of hypoglycaemia with concomitant blood glucose measurements below 70.
 - All occurrences of hypoglycemia will be treated with orange juice, 3-4 glucose tablets, or a 20% glucose solution via an I.V. bolus injection over 1 to 2 minutes and the subject will be monitored until symptoms have resolved.
 - If three or more finger stick glucose values of <50 mg/dL (2.78 mmol/L) are observed in one week within 12 hours subsequent to administration of study drug without a reasonable explanation (such as increased physical activity and/or skipped meal), the patient will be discontinued from treatment with study drug. This information will be recorded in the patient's diary and the patient will be instructed to contact the study site if this occurs. The patient will continue to be seen for all remaining study visits.
 - The site will instruct patients to immediately perform a finger stick glucose measurement if any symptoms occur that may be related to hypoglycemia (e.g., weakness, dizziness, shakiness, increased sweating, palpitations, or confusion), and to avoid delay in treating these symptoms. The measurements will be recorded in the patient diary.
 - Patients will always carry glucose tablets with them and ingest 3-4 tablets if hypoglycemia necessitates it.

REFERENCES

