Definite: The event follows a reasonable temporal sequence from the time of active study drug administration, follows a known response pattern to the drug, cannot be reasonably explained by other factors such as the patient’s condition, concomitant drugs or therapeutic interventions, AND either occurs immediately following active study drug administration, improves on stopping the study drug, or reappears on re-exposure.

Adverse Events of Hypoglycemia

The CTCAE (version 4.0) criteria for mild, moderate, and severe hypoglycemia based on blood glucose will be used, as shown below:

Mild: < 70 – 55 mg/dL (< 3.8 - 3.0 mmol/L)

Moderate: < 55 – 40 mg/dL (< 3.0 - 2.2 mmol/L)

Severe: < 40 – 30 mg/dL (< 2.2 - 1.7 mmol/L)

Life Threatening: < 30 mg/dL (< 1.7 mmol/L)

Recording Adverse Events

All adverse events experienced during the trial, regardless of relationship to study medication, must be recorded on the Adverse Event CRF from the time of patient consent until completion of patients End of Study visit (Visit 9). All serious adverse events will be collected through Visit 9. The Investigator must continue to follow all non-serious events possibly related to the study medication and all serious adverse events until they resolve or until the Investigator assesses them in writing as chronic or stable.

Regardless of relationship to study medication, the event must be recorded on the Adverse Event CRF. Adverse event documentation should include the following information:

- Standard medical terminology for the AE
- Description of adverse event
- Date and time of onset
- Date and time of resolution of the adverse event
- Whether or not the event is ongoing
- Severity of the event
- Relationship between the adverse event and the investigational product
- Description of any actions taken (e.g., medications, treatments)
- Outcome of the AE
- Whether or not the effect was serious and/or unanticipated

Whenever possible, a diagnosis should be given when signs and symptoms are due to common etiology (e.g., cough, runny nose, sneezing, sore throat, and head congestion should be reported as "upper respiratory infection"). For the purposes of this study, hypoglycemic events will be considered adverse events and should be recorded in source and CRF records.

When a diagnosis is not available, each adverse event should be reported separately. For example, "nausea and vomiting" should be split into two separate events.

Reporting Serious Adverse Events

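### The hypoglycaemia stop rule has no deeper tier: one or two readings below 40 mg/dL lead to no default decision on study drug and no explicit instruction to contact the site

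*Protocol*

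**What the plan says.** The discontinuation rule for low glucose appears twice.

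- **Safety Evaluations:** "If three or more finger stick glucose values of <50 mg/dL (2.78 mmol/L) are observed in one week within 12 hours" of dosing, with no reasonable explanation such as exercise or a missed meal, the patient comes off study drug.
- **Self-Monitoring Fasting Blood Glucose and Patient Diaries:** the same threshold and count, but no weekly window: "if three or more are observed within 12 hours subsequent to administration of study drug without a reasonable explanation". Only this section adds a laboratory step: "Fingerstick glucose values of <50 mg/dL (2.78 mmol/L) should be confirmed by laboratory plasma glucose measurements".

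In both places the contact instruction, "the patient will be instructed to contact the study site if this occurs", comes after the three-reading sentence.

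Appendix B (Adverse Events of Hypoglycemia) grades events by glucose level. Moderate runs from below 55 down to 40 mg/dL, Severe from below 40 down to 30, and the last band is "Life Threatening: < 30 mg/dL (< 1.7 mmol/L"). No grade is linked to an action on study drug.

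Other provisions that bear on a very low reading:

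- Every hypoglycaemic episode is treated with glucose and the subject is monitored until symptoms resolve (Safety Evaluations).
- Hypoglycaemic events count as adverse events, and the investigator assesses each adverse event for seriousness, severity and relatedness (Appendix B).
- Serious or otherwise medically significant events go to the sponsor within 24 hours (Appendix B).
- Home readings reach the site through the diary: "Patients will be required to record the values in a patient diary and bring the diary to each clinic visit". Visits after the start of dosing are "outpatient visits at week 1, 2, 4, 8, and 12 (final visit").
- On dosing: "Patients will take 2 capsules daily in the morning with or without food".

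**The concern.** Safety is the primary objective, and hypoglycaemia is the main risk that the Protocol names for this product. The Protocol has a four-level depth scale, but its one mandatory stop uses a single cut-off plus a count of three. After one home reading below 40 mg/dL, the text does not say whether the patient takes the next morning's capsules. Nor does it plainly tell the patient to let the site know.

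High glucose is handled differently. One self-monitored value of 270 mg/dL or more obliges the patient to contact the clinic, and a stop follows if the repeat is also high. So the Protocol has a single-value contact rule for high readings and no equally explicit one for dangerously low readings.

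The two versions of the low-glucose rule also differ, in the weekly window and in the laboratory step. Site staff and patient instructions could therefore follow different rules.

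**Working it through.** **1. Threshold check.** 50 mg/dL ÷ 18.016 = 2.78 mmol/L, as the Protocol states.

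**2. Overlap with the grading scale.** The rule counts values below 50; Moderate covers 40 to below 55. Moderate readings of 40 to 49 therefore count, and readings of 50 to 54 are Moderate but never count. All Severe and Life Threatening readings count, but each counts as one, the same as a reading of 49.

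**3. The rule applied to example readings.** Three interpretations of the window were tried: any one week (Safety Evaluations), the 12 hours after a single dose (strict reading of the self-monitoring section), and no outer limit (loose reading of the same section). Unless stated otherwise, readings are unexplained and within 12 hours of a dose.

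| Readings (mg/dL) | Grade | One week | After one dose | No outer limit |
|---|---|---|---|---|
| 49, 49, 49, same day | Moderate | stop | stop | stop |
| 45, 45, 45, over 5 days | Moderate | stop | no stop | stop |
| 35, once or twice | Severe | no stop | no stop | no stop |
| 25, once or twice | Life Threatening | no stop | no stop | no stop |
| 25, 25, 25, all explained, or all more than 12 hours after dose | Life Threatening | no stop | no stop | no stop |

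The result for one or two deep readings is the same under every interpretation. The second row shows that the difference in wording matters for the recurrence rule itself.

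**4. How long a home reading could wait.** Visits at weeks 0, 1, 2, 4, 8 and 12 give gaps of 7, 7, 14, 28 and 28 days, which sum to 84. The two 28-day gaps cover 56 of the 84 treatment days. With the ±2-day windows in Table 1, the gap between the week 4 and week 8 visits runs from day 30 to day 54 (24 days) up to day 26 to day 58 (32 days).

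The regimen is 2 × 8 mg = 16 mg once daily. A reading on the day of the week 4 visit, after the visit, could be followed by 28 further doses (days 29 to 56), or 24 to 32 with the windows, before the next scheduled diary review. This needs two things to go wrong: the patient does not call, and the laboratory confirmation step does not happen.

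**5. Do the other provisions close the gap?** Glucose treatment and monitoring deal with the episode. Laboratory confirmation has no stated consequence after one or two values. Investigator assessment covers seriousness, severity and relatedness, not continuation of dosing. The 24-hour report of a serious event runs from when the site is notified, so it cannot shorten a delay in the site hearing of the event, and it mandates no dosing action.

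**The case against.** The best defence is that this is a reasonable choice for a small, open-label pilot at one centre. The treating investigator may stop drug at any time, and exclusion criterion 14 keeps out antidiabetic drugs other than metformin, so deep lows should be uncommon. The high-glucose rule also requires a repeat before a forced stop and has no deeper tier: one value of 500 mg/dL mandates no hold. Requiring recurrence looks consistent. This stands as a reason not to call the rule an error. It does not supply a default for a patient at home before the next morning's dose, and the high-glucose rule at least makes contact explicit.

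Four stronger readings are tempting, and the Protocol does not support them.

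- *The stop rule ignores depth.* It does not: below 50 mg/dL is a depth cut-off, and it excludes all Mild and some Moderate readings. What is missing is a second tier.
- *The stop rule contradicts Appendix B.* Appendix B grades adverse events; it does not set dosing rules.
- *A very low reading gets no review.* Appendix B requires the investigator to assess every adverse event, including each hypoglycaemic event. What is missing is a required decision on study drug.
- *Patients will go weeks without the site knowing.* Confirming a home value in the laboratory implies reaching the site. The 28 doses arise only if that step fails and the patient does not call. The Protocol gives no probability for this.

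**Conclusion.** The point holds in this form. The only mandatory hypoglycaemia stop needs three or more unexplained readings below 50 mg/dL within 12 hours of dosing. After one or two readings below 40 mg/dL, including below 30, the Protocol sets no default on study drug and gives no explicit instruction to contact the site. This follows directly from the text and does not depend on which window is used.

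The exposure figure of 28 further doses (24 to 32 with visit windows) is an upper bound, conditional on no call and no laboratory confirmation. It measures how long notification could lapse; it is neither an expected delay nor a measure of harm.

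The frequency of such readings is probably low, and the Protocol gives no basis for estimating it. Of the two hypoglycaemia entries in the Appendix A Phase IIb table, one lists a blood sugar of 12.0 mmol/L and the other rests on clinical symptoms alone.

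Because safety is the primary objective and the remedy is short, this should be fixed.

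**What to change.** Replace both versions of the rule with one paragraph, used identically in the self-monitoring section, in Safety Evaluations and in the patient instructions.

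- **Recurrence rule.** Keep three or more unexplained values below 50 mg/dL within 12 hours of dosing in one week, with laboratory confirmation where feasible.
- **Any single finger-stick value below 40 mg/dL.** The patient treats it, contacts the site the same day and holds study drug until the investigator has reviewed it and documented a decision to resume or stop.
- **Any value below 30 mg/dL.** The default is to stop, unless a meter error is shown or the investigator documents why resuming is safe.
- **Laboratory result.** A normal sample drawn after glucose treatment does not by itself rule out the low reading, so it should not end the hold without investigator review.
- **Explained readings.** A skipped meal or exercise may support resuming, but does not waive contact and review.

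The cost is one amendment paragraph, the matching change to patient instructions, and possibly a few more temporary interruptions, whose number cannot be estimated from the Protocol. A meter error would cost a short hold, not the patient's treatment.

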APPENDIX A: Studies of Oramed Oral Insulin in Humans

Phase 1A Clinical Trial

[figure not shown]
The encouraging outcome of the pre-clinical studies set the stage for Phase 1a clinical trials that evaluated oral insulin on eight healthy male volunteers during four separate visits. The study was completed in August of 2007. The results of this study clearly demonstrated that the insulin administered by Oramed's capsules was absorbed and retained its biological activity. Additionally, it exhibits unique PK and PD effects characterized by the delayed onset of action and a prolonged metabolic effect as compared with other oral or inhaled formulations currently under study.

Phase 1B Clinical Trial

Oramed then continued with a formulation optimization (Phase 1b) clinical trial which included eight healthy male volunteers studied during five visits. The trials were completed in March of 2008 and the results showed again that insulin combined with Oramed's drug delivery enhancers and formulated in a capsule dosage form was absorbed and resulted in plasma glucose reduction, a decrease in c-peptide and an increase in insulin. A lead formulation was identified as a result of this study.

Phase 2A– Type 2 Diabetes Mellitus Clinical Trial

In August 2008, Oramed completed Phase 2a clinical trials of ORMD 0801. The trial included ten Type 2 diabetic patients studied over the course of seven visits. The goal of these trials was to evaluate the safety and efficacy of oral insulin on patients with diabetes. The results of this clinical trial showed that Oramed's oral insulin capsule can effectively deliver insulin to people with diabetes and result in lowering blood glucose levels. Furthermore oral insulin (ORMD 0801) was found safe and was well tolerated.

Figures A-D: **A.** Representative glucose and insulin recordings of an ORMD 0801 responder over the 5hrs of testing. **B.** Representative glucose and insulin recordings of a placebo-treated subject over the 5 hrs of testing. **C.** Representative c-peptide and insulin recordings of an ORMD 0801 responder. **D.** AUC₁₂₀₋₁₈₀ and AUC₁₈₀₋₂₄₀ calculations presented as ratios of AUC₀₋₆₀ of both glucose and c-peptide levels following ORMD 0801 and placebo treatments.

Phase 2A– Type 1 Diabetes Mellitus – Clinical Trial

Phase IIb – Type 2 Diabetes Mellitus - Clinical Trial

This multi-site, placebo-controlled, randomized, double-blinded study, conducted in South Africa, focused on the responses of 29 Type II diabetes (T2DM) patients to ORMD-0801. Volunteers received a once-daily, fixed dose of oral insulin capsules (8 mg/capsule, 2 capsules = 16 mg/day) for a period of six weeks. Three of the subjects were otherwise on diet, while 27 were on diet+Metformin (≥ 2.5 g/day) diabetes management programs before the study. The primary objective of this trial was to assess the safety and tolerability of the investigational product, by monitoring adverse events, hypoglycemia and other safety parameters throughout the study. Secondary endpoints evaluated the effectiveness of ORMD-0801 in providing glycemic control, as determined by comparison of baseline fasting blood glucose (FBG), insulin, fructosamine, c-peptide, C-reactive protein (CRP) and Hb1Ac levels to those measured after the 6-week treatment period.

The 6-week ORMD-0801 treatment regimen proved safe and tolerable, with no reports of serious AEs throughout the study period. No cumulative effects of extended exposure to

ORMD-0801 were observed, and only two mild hypoglycemic events were recorded in patient diaries (Table 1).

Table 1: Adverse Events ORMD-0801 Cohort*

Event	Severity	Action	Outcome	Notes
Hypoglycaemia	Mild	Dose not changed	Recovered	Blood sugar: 12.0 mmol/L
Hypoglycaemia	Unknown	Unknown	Unknown	Hypoglycaemic on clinical symptoms
Constipation	Mild	Dose not changed	Not recovered	
Diarrhoea and skin rash	Mild	Dose not changed	Recovered	
Diarrhoea	Mild	Dose not changed	Recovered	
Increased bowel movement	Mild	Not applicable	Recovered	

* no AEs were reported in the placebo cohort

Efficacy evaluations were performed on blood samples of 21 patients on oral insulin and 8 patients on placebo. Mean decreases in insulin and CRP levels were found to be statistically significant following the 6-week, once-daily ORMD-0801 treatment period, when compared to the placebo group (Figure 6A). These findings suggest that ORMD-0801 offered temporary relief to insulin-secreting beta cells. Moreover, the percentage of subjects demonstrating clinically relevant reductions in insulin, c-peptide, FBG and Hb1Ac levels was always higher in the ORMD-0801 cohort, when compared to the placebo (Figure 6B).

[figure not shown]

Figure 6. Plasma marker responses and percent responders to a six-week, daily oral ORMD-0801 regimen T2DM patients were treated once daily with a 16 mg insulin ORMD-0801 formulation or placebo capsule. Blood samples drawn at the start of the study and after a 6-week treatment period were tested for marker levels. A. Mean changes (\pm SD) in plasma insulin and CRP levels between the samples of day 0 and samples taken after the 6-wk treatment period are presented. B. Subjects demonstrating a decrease of ≥ 0.5 mmol/L in FBG, ≥ 40 μ mol/L fructose-amine, $\geq 0.6\%$ Hb1Ac, ≥ 1 mU/L insulin, ≥ 100 pmol/L c-peptide or ≥ 1 mg/L CRP were considered responders for that specific marker. The number of responders for each tested marker is presented as the percent of the total number of subjects analyzed for the given parameter.

Further investigation involving univariate, covariate and multivariate analyses, demonstrated positive correlations between above-average recordings of subject baseline triglyceride, BMI, insulin, HbA1c, c-peptide or blood pressure and/or below borderline-high levels of baseline cholesterol or LDL, and increased CRP responses (Table 2). When only considering individuals presenting these predictors (72.4-75.9% of the original study population), more significant decreases in CRP levels than those obtained for the full intent-to-treat (ITT) population, were observed following insulin-based treatment, when compared to placebo. In these cases, mean intercohort differences in CRP levels ranged between 73.9-87.6% (p-values: 0.022-0.007), demonstrating a strong impact of the oral insulin preparation on inflammatory response with expected influence on insulin sensitivity.

Table 2. Clinically relevant predictors for heightened CRP responses among T2DM patients											
	Predictor	ORMD-0801 (N)	Placebo (N)	Percent of ITT population (%)	Mean change ORMD-0801	Mean change placebo	SD change ORMD-0801	SD change placebo	Difference between cohorts using the optimal rule (%)	p-Value Under Optimal Rule	Adjusted p-Value Optimal Rule
1	0.86 <= BASELINE_TRI <= 3.11	13	8	72.4	-1.3385	3.05	2.032	3.1625	-73.90%	0.0138	0.0036
2	7.5 <= BASELINE_HBA1C <= 10.1	16	7	79.3	-0.9875	3.5571	2.3984	3.1796	-76.50%	0.014	0.0056
3	27.1 <= VS_BMI	15	7	75.9	-1.0533	3.5571	2.4969	3.1796	-77.60%	0.0153	0.0052
4	BASELINE_CHOLESTEROL <= 6.15	17	5	75.9	-0.4647	4.54	2.2803	3.408	-84.30%	0.0159	0.0054
5	1.39 <= BASELINE_LDL <= 4.17	16	5	72.4	-0.3125	4.54	2.2516	3.408	-81.70%	0.0217	0.0067
6	123 <= VS_BP_SYS	16	6	75.9	-0.3438	4.1167	1.8812	3.15	-75.10%	0.0076	0.0021
7	123 <= VS_BP_SYS AND BASELINE_HDL <= 1.73	16	5	72.4	-0.3438	4.86	1.8812	3.152	-87.60%	0.0038	0.0006
8	123 <= VS_BP_SYS AND 493 <= BASELINE_CPEP	15	6	72.4	-0.5333	4.1167	1.8089	3.15	-78.30%	0.0065	0.0013
9	123 <= VS_BP_SYS AND BASELINE_HDL <= 1.73	16	5	72.4	-0.3438	4.86	1.8812	3.152	-87.60%	0.0038	0.0006
10	123 <= VS_BP_SYS AND 6.4 <= BASELINE_INSULIN	16	5	72.4	-0.3438	4.86	1.8812	3.152	-87.60%	0.0038	0.0006
11	123 <= VS_BP_SYS AND 493 <= BASELINE_CPEP	15	6	72.4	-0.5333	4.1167	1.8089	3.15	-78.30%	0.0065	0.0013
12	7.5 <= BASELINE_HBA1C <= 10.1 AND 30 <= AGE	15	7	75.9	-1.3733	3.5571	2.1982	3.1796	-83.00%	0.0071	0.0019
13	123 <= VS_BP_SYS AND 1 YR <= METFORMIN_DURATION	16	5	72.4	-0.3438	4.54	1.8812	3.408	-82.20%	0.0073	0.0015

The reported results substantiate the safety and tolerability of ORMD-0801 and demonstrate a relevant clinical impact of ORMD-0801 at the tested dose. The small sample size and placebo effect, thoroughly described in the literature for diabetes management studies, contributed to the often nonsignificant outcomes in baseline vs. post-treatment marker levels. However, this first analysis of long-term exposure to ORMD-0801, proved its safety and tolerability, and will lay the foundation for further testing in larger populations. In addition, the findings related to CRP responses present factors which may be essential in further understanding interpatient insulin response variability, which to date, has challenged healthcare providers in outlining effective glucose control protocols. Definition of highly responsive subject subpopulations is expected to enhance insulin-based treatment efficacy.

